### 7.3 Assessing and Recording Adverse Events

An adverse event is defined as any untoward medical occurrence in a patient or clinical investigation subject administered a pharmaceutical product and which does not necessarily have to have a causal relationship with this treatment. An adverse event can therefore be any unfavorable and unintended sign (including an abnormal laboratory finding, for example), symptom, or disease temporally associated with the use of a medicinal product or protocol-specified procedure, whether or not considered related to the medicinal product or protocol-specified procedure. Any worsening (i.e., any clinically significant adverse change in frequency and/or intensity) of a preexisting condition that is temporally associated with the use of the Merck's product, is also an adverse event.

Changes resulting from normal growth and development that do not vary significantly in frequency or severity from expected levels are not to be considered adverse events. Examples of this may include, but are not limited to, teething, typical crying in infants and children and onset of menses or menopause occurring at a physiologically appropriate time. Merck product includes any pharmaceutical product, biological product, device, diagnostic agent or protocol-specified procedure, whether investigational (including placebo or active comparator medication) or marketed, manufactured by, licensed by, provided by or distributed by Merck for human use.

Adverse events may occur during the course of the use of Merck product in clinical trials, or as prescribed in clinical practice, from overdose (whether accidental or intentional), from abuse and from withdrawal.

Progression of the cancer under study is not considered an adverse event.

All adverse events that occur after the consent form is signed but before treatment allocation must be reported by the investigator if they cause the subject to be excluded from the trial, or are the result of a protocol-specified intervention, including but not limited to washout or discontinuation of usual therapy, diet, placebo treatment or a procedure.

From the time of treatment allocation through 30 days following cessation of treatment, all adverse events must be reported by the investigator. Such events will be recorded at each examination on the Adverse Event case report forms/worksheets. The reporting timeframe for adverse events meeting any serious criteria is described in section 7.3.3.1. The investigator will make every attempt to follow all subjects with non-serious adverse events for outcome.

Adverse events will not be collected for subjects during the pre-screening period (for determination of archival tissue status) as long as that subject has not undergone any protocol-specified procedure or intervention. If the subject requires a blood draw, fresh tumor biopsy etc., the subject is first required to provide consent to the main study and AEs will be captured according to guidelines for standard AE reporting.

### **7.3.1 Definition of an Overdose for This Protocol and Reporting of Overdose to the Sponsor and to Merck**

For purposes of this trial, an overdose of pembrolizumab will be defined as any dose of 1,000 mg or greater ( $\geq 5$  times the indicated dose). No specific information is available on the treatment of overdose of pembrolizumab. Appropriate supportive treatment should be provided if clinically indicated. In the event of overdose, the subject should be observed closely for signs of toxicity. Appropriate supportive treatment should be provided if clinically indicated.

If an adverse event(s) is associated with (“results from”) the overdose of a Merck product, the adverse event(s) is reported as a serious adverse event, even if no other seriousness criteria are met.

If a dose of Merck’s product meeting the protocol definition of overdose is taken without any associated clinical symptoms or abnormal laboratory results, the overdose is reported as a non-serious Event of Clinical Interest (ECI), using the terminology “accidental or intentional overdose without adverse effect.”

**All reports of overdose with and without an adverse event must be reported within 24 hours to the Sponsor and within 2 working days hours to Merck Global Safety. (Attn: Worldwide Product Safety; [contact])**

### **7.3.2 Reporting of Pregnancy and Lactation to the Sponsor and to Merck**

Although pregnancy and lactation are not considered adverse events, it is the responsibility of investigators or their designees to report any pregnancy or lactation in a subject (spontaneously reported to them) that occurs during the trial.

Pregnancies and lactations that occur after the consent form is signed but before treatment allocation must be reported by the investigator if they cause the subject to be excluded from the trial, or are the result of a protocol-specified intervention, including but not limited to washout or discontinuation of usual therapy, diet, placebo treatment or a procedure.

Pregnancies and lactations that occur from the time of treatment allocation through 120 days following cessation of Sponsor’s product, or 30 days following cessation of treatment if the subject initiates new anticancer therapy, whichever is earlier, must be reported by the investigator. All reported pregnancies must be followed to the completion/termination of the pregnancy. Pregnancy outcomes of spontaneous abortion, missed abortion, benign hydatidiform mole, blighted ovum, fetal death, intrauterine death, miscarriage and stillbirth must be reported as serious events (Important Medical Events). If the pregnancy continues to term, the outcome (health of infant) must also be reported.

Such events must be reported within 24 hours to the Sponsor and within 2 working days to Merck Global Safety. (Attn: Worldwide Product Safety; [contact])

### 7.3.3 Immediate Reporting of Adverse Events to the Sponsor and to Merck

#### 7.3.3.1 Serious Adverse Events

A serious adverse event is any adverse event occurring at any dose or during any use of Merck's product that:

- Results in death;
- Is life threatening;
- Results in persistent or significant disability/incapacity;
- Results in or prolongs an existing inpatient hospitalization;
- Is a congenital anomaly/birth defect;
- Is another important medical event

**Note:** In addition to the above criteria, adverse events meeting either of the below criteria, although not serious per ICH definition, are reportable to the Merck in the same timeframe as SAEs to meet certain local requirements. Therefore, these events are considered serious by Merck for collection purposes.

- Is a new cancer (that is not a condition of the study);
- Is associated with an overdose.

Refer to Table 6 for additional details regarding each of the above criteria.

For the time period beginning when the consent form is signed until treatment allocation, any serious adverse event, or follow up to a serious adverse event, including death due to any cause other than progression of the cancer under study (reference Section 7.3.3.3 for additional details) that occurs to any subject must be reported within 24 hours to the Sponsor and within 2 working days to Merck Global Safety if it causes the subject to be excluded from the trial, or is the result of a protocol-specified intervention, including but not limited to washout or discontinuation of usual therapy, diet, placebo treatment or a procedure.

For the time period beginning at treatment allocation through 90 days following cessation of treatment, or 30 days following cessation of treatment if the subject initiates new anticancer therapy, whichever is earlier, any serious adverse event, or follow up to a serious adverse event, including death due to any cause other than progression of the cancer under study (reference Section 7.3.3.3 for additional details), whether or not related to the Merck product, must be reported within 24 hours to the Sponsor and within 2 working days to Merck Global Safety.

Additionally, any serious adverse event, considered by an investigator who is a qualified physician to be related to Merck product that is brought to the attention of the investigator at any time following consent through the end of the specified safety follow-up period specified in the paragraph above, or at any time outside of the time period specified in the previous paragraph also must be reported immediately to the Sponsor and to Merck Global Safety.

All subjects with serious adverse events must be followed up for outcome.

**SAE reports and any other relevant safety information are to be forwarded to the Merck Global Safety [contact]**

A copy of all 15 Day Reports and Annual Progress Reports is submitted as required by FDA, European Union (EU), Pharmaceutical and Medical Devices agency (PMDA) or other local regulators. Investigators will cross-reference this submission according to local regulations to the Merck Investigational Compound Number (IND, CSA, etc.) at the time of submission. Additionally investigators will submit a copy of these reports to Merck & Co., Inc. (Attn: Worldwide Product Safety; [contact]) at the time of submission to FDA.

### 7.3.3.2 Events of Clinical Interest

Selected non-serious and serious adverse events are also known as Events of Clinical Interest (ECI) and must be reported within 24 hours to the Sponsor and within 2 working days to Merck Global Safety. (Attn: Worldwide Product Safety; [contact]).

For the time period beginning when the consent form is signed until treatment allocation, any ECI, or follow up to an ECI, that occurs to any subject must be reported within 24 hours to the Sponsor and within 2 working days to Merck Global Safety if it causes the subject to be excluded from the trial, or is the result of a protocol-specified intervention, including but not limited to washout or discontinuation of usual therapy, diet, placebo treatment or a procedure.

For the time period beginning at treatment allocation through 90 days following cessation of treatment, or 30 days following cessation of treatment if the subject initiates new anticancer therapy, whichever is earlier, any ECI, or follow up to an ECI, whether or not related to Merck product, must be reported within 24 hours to the Sponsor and within 24 hours to Merck Global Safety.

#### Events of clinical interest for this trial include:

1. an overdose of Merck product, as defined in Section 7.3.1 - Definition of an Overdose for This Protocol and Reporting of Overdose to the Sponsor, that is not associated with clinical symptoms or abnormal laboratory results.
2. an elevated AST or ALT lab value that is greater than or equal to 3X the upper limit of normal and an elevated total bilirubin lab value that is greater than or equal to 2X the upper limit of normal and, at the same time, an alkaline phosphatase lab value that is less than 2X the upper limit of normal, as determined by way of protocol-specified laboratory testing or unscheduled laboratory testing.\*

\*Note: These criteria are based upon available regulatory guidance documents. The purpose of the criteria is to specify a threshold of abnormal hepatic tests that may require an additional evaluation for an underlying etiology.

### 7.3.3.3 Protocol-Specific Exceptions to Serious Adverse Event Reporting

Efficacy endpoints as outlined in this section will not be reported to Merck as described in Section 7.3.3, *Immediate Reporting of Adverse Events to the Sponsor and to Merck*, unless there is evidence suggesting a causal relationship between the drug and the event. Any such event will be submitted to the Sponsor within 24 hours and to Merck Global Safety within 2 working days either by electronic or paper media.

Specifically, the suspected/actual events covered in this exception include any event that is disease progression of the cancer under study.

The Sponsor will monitor unblinded aggregated efficacy endpoint events and safety data to ensure the safety of the subjects in the trial. Any suspected endpoint which upon review is not progression of the cancer under study will be forwarded to Merck Global Safety as a SAE within 2 working days of determination that the event is not progression of the cancer under study. Hospitalization related to convenience (e.g. transportation issues etc.) will not be considered a SAE.

#### **7.3.4 Evaluating Adverse Events**

An investigator who is a qualified physician will evaluate all adverse events according to the NCI Common Terminology for Adverse Events (CTCAE), version 4.03. Any adverse event which changes CTCAE grade over the course of a given episode will have each change of grade recorded on the adverse event case report forms/worksheets. All adverse events regardless of CTCAE grade must also be evaluated for seriousness.

**Table 7. Evaluating Adverse Events**

An investigator who is a qualified physician, will evaluate all adverse events as to:

V4.03 CTCAE Grading	Grade 1	Mild; asymptomatic or mild symptoms; clinical or diagnostic observations only; intervention not indicated.
	Grade 2	Moderate; minimal, local or noninvasive intervention indicated; limiting age-appropriate instrumental ADL.
	Grade 3	Severe or medically significant but not immediately life-threatening; hospitalization or prolongation or hospitalization indicated; disabling; limiting self-care ADL.
	Grade 4	Life threatening consequences; urgent intervention indicated.
	Grade 5	Death related to AE
Seriousness	A serious adverse event is any adverse event occurring at any dose or during any use of Merck product that:	
	† Results in death ; or	
	† Is life threatening ; or places the subject, in the view of the investigator, at immediate risk of death from the event as it occurred (Note: This does not include an adverse event that, had it occurred in a more severe form, might have caused death.); or	
	† Results in a persistent or significant disability/incapacity (substantial disruption of one's ability to conduct normal life functions); or	
	† Results in or prolongs an existing inpatient hospitalization (hospitalization is defined as an inpatient admission, regardless of length of stay, even if the hospitalization is a precautionary measure for continued observation. (Note: Hospitalization for an elective procedure to treat a pre-existing condition that has not worsened is not a serious adverse event. A pre-existing condition is a clinical condition that is diagnosed prior to the use of a Merck product and is documented in the patient's medical history.); or	
	† Is a congenital anomaly/birth defect (in offspring of subject taking the product regardless of time to diagnosis); or	
	Is a new cancer (that is not a condition of the study) (although not serious per ICH definition, is reportable to the Sponsor within 24 hours and to Merck within 2 working days to meet certain local requirements); or	
	Is an overdose (whether accidental or intentional). Any adverse event associated with an overdose is considered a serious adverse event for collection purposes. An overdose that is not associated with an adverse event is considered a non-serious event of clinical interest and must be reported within 24 hours to the Sponsor and to Merck within 2 working days.	

	
Other important medical events that may not result in death, not be life threatening, or not require hospitalization may be considered a serious adverse event when, based upon appropriate medical judgment, the event may jeopardize the subject and may require medical or surgical intervention to prevent one of the outcomes listed previously (designated above by a †).

Duration	Record the start and stop dates of the adverse event. If less than 1 day, indicate the appropriate length of time and units
Action taken	Did the adverse event cause Merck product to be discontinued?
Relationship to Merck Product	
Did Merck product cause the adverse event? The determination of the likelihood that Merck product caused the adverse event will be provided by an investigator who is a qualified physician. The investigator's signed/dated initials on the source document or worksheet that supports the causality noted on the AE form, ensures that a medically qualified assessment of causality was done. This initialed document must be retained for the required regulatory time frame. The criteria below are intended as reference guidelines to assist the investigator in assessing the likelihood of a relationship between the test drug and the adverse event based upon the available information.
 
The following components are to be used to assess the relationship between Merck product and the AE; the greater the correlation with the components and their respective elements (in number and/or intensity), the more likely Merck product caused the adverse event (AE):
 
Exposure Is there evidence that the subject was actually exposed to Merck product such as: reliable history, acceptable compliance assessment (pill count, diary, etc.), expected pharmacologic effect, or measurement of drug/metabolite in bodily specimen?
 
Time Course Did the AE follow in a reasonable temporal sequence from administration of Merck product? Is the time of onset of the AE compatible with a drug-induced effect (applies to trials with investigational medicinal product)?
 
Likely Cause Is the AE not reasonably explained by another etiology such as underlying disease, other drug(s)/vaccine(s), or other host or environmental factors

Relationship to Merck Product (continued)	The following components are to be used to assess the relationship between the test drug and the AE: (continued)	
	Dechallenge	Was Merck product discontinued or dose/exposure/frequency reduced? If yes, did the AE resolve or improve? If yes, this is a positive dechallenge. If no, this is a negative dechallenge. (Note: This criterion is not applicable if: (1) the AE resulted in death or permanent disability; (2) the AE resolved/improved despite continuation of the Sponsor's product; or (3) the trial is a single-dose drug trial); or (4) Sponsor's product(s) is/are only used one time.)
	Rechallenge	Was the subject re-exposed to Merck product in this study? If yes, did the AE recur or worsen? If yes, this is a positive rechallenge. If no, this is a negative rechallenge. (Note: This criterion is not applicable if: (1) the initial AE resulted in death or permanent disability, or (2) the trial is a single-dose drug trial); or (3) Sponsor's product(s) is/are used only one time). NOTE: IF A RECHALLENGE IS PLANNED FOR AN ADVERSE EVENT WHICH WAS SERIOUS AND WHICH MAY HAVE BEEN CAUSED BY MERCK PRODUCT, OR IF REEXPOSURE TO MERCK PRODUCT POSES ADDITIONAL POTENTIAL SIGNIFICANT RISK TO THE SUBJECT, THEN THE RECHALLENGE MUST BE APPROVED IN ADVANCE BY THE SPONSOR AS PER DOSE MODIFICATION GUIDELINES IN THE PROTOCOL.
Consistency with Trial Treatment Profile	Is the clinical/pathological presentation of the AE consistent with previous knowledge regarding Merck product or drug class pharmacology or toxicology?	
The assessment of relationship will be reported on the case report forms /worksheets by an investigator who is a qualified physician according to his/her best clinical judgment, including consideration of the above elements.		
Record one of the following	Use the following scale of criteria as guidance (not all criteria must be present to be indicative of Merck product relationship).	
Yes, there is a reasonable possibility of Merck product relationship.	There is evidence of exposure to Merck product. The temporal sequence of the AE onset relative to the administration of Merck product is reasonable. The AE is more likely explained by Merck product than by another cause.	
No, there is not a reasonable possibility of Merck product relationship	Subject did not receive the Merck product OR temporal sequence of the AE onset relative to administration of Merck product is not reasonable OR the AE is more likely explained by another cause than the Merck product. (Also entered for a subject with overdose without an associated AE.)	

### 7.3.5 Sponsor Responsibility for Reporting Adverse Events

All Adverse Events will be reported to regulatory authorities, IRB/IECs and investigators in accordance with all applicable global laws and regulations.

## 8 STATISTICAL ANALYSIS PLAN

### 8.1 Introduction

This study has two parts:

- a. Phase I dose-escalation to determine the recommended phase II dose of Poly-ICLC to be combined with the standard dose of pembrolizumab. Patients with any solid tumor that is unresponsive to at least two lines of therapy is eligible for the dose escalation phase unless curative options exist.
- b. The combination will then be administered at the recommended phase II dose to in up to 27 patients with relapsed metastatic colon cancer. MSI-high patients will be excluded.

Descriptive statistics will be presented for primary and secondary endpoints. Summary statistics for continuous variables will include the mean, standard deviation, median, and range (minimum/maximum). Categorical variables will be presented as frequency counts and percentages; and time-to-event variables will be summarized by Kaplan-Meier medians and survival plots. Data listings will be created to support each table and to present all data. The data will be tabulated and analyzed with respect to patient enrollment and disposition, demographic and baseline characteristics, for primary efficacy and safety measures per study part (Phase I, II), and on a per dose level for phase I part. The primary efficacy analysis will be conducted on the efficacy evaluable population and safety analysis will be performed on the safety evaluable population. Maximum tolerated dose for of Poly-ICLC to be combined with pembrolizumab will be estimated based on the data from the 3+3 dose escalation. RP2D will then be determined based on the estimated MTD, which should not exceed 1/6 of RLT. SAS 9.3 software, or higher will be used for data analysis.

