#### 2) Phase II trial expansion

[figure not shown]
- a. The combination will then be administered at the recommended phase II dose in up to 27 patients with metastatic MRP colon cancer

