### **5.10 Subject Replacement Strategy**

Subjects who withdraw from therapy prior to completion of cycle 1 of therapy will be replaced during the phase I portion of the trial to allow for evaluation of at least 3 subjects at each dose level. Similarly, if patients withdraw before assessment of tumor response in the phase II portion of the trial, they will be replaced unless withdrawal is due to clinical disease progression.

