### 8.4 Sample Size/Accrual Rate

For part 1: 3 to 12 patients will be used for the dose escalation part. The actual number of patients will depend on the DLT and MTD. We are expecting 3 patients per month to be enrolled in the study.

For Part 2: With the assumption that the RR rate for pembrolizumab alone is about  $H_0=5\%$ , 27 patients are needed to detect an increase in RR to  $H_1=20\%$  for the treatment combination to achieve 80% power and keep the probability of type I error ( $\alpha$ ) at 0.05. We are expecting accrual rate of 5 patients per month during the phase II portion of the study.

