### 8.5 Analysis of Endpoints

#### 8.5.1 Analysis of Primary Endpoints

- a. A minimum of 3 patients will be treated depending on DLT. Dose level 1 (1mg) will be administered to a cohort of 3 patients. If 0 out of 3 experience DLT, then dose escalation will proceed to the dose level 2 (2mg). If one out of three patients experience DLT, a cohort of additional three patients will be assigned to the same dose level (1mg). If two or more patients of three (or six) patients experience DLT at the first dose level, the trial, then enrollment of patients will be stopped. If a maximum one patient experience DLT at dose level 2, then the dose will be declared the RP2D. If 2 or more out of 6 patients experience DLT at the second dose level, then the first dose level (1mg) will be declared the RD2D. The RP2D should have at least 6 patients enrolled at the dose level with a maximum of 1 patient experiencing DLT.
- b. To assess preliminary evidence of antitumor activity, in terms of Objective Response Rate (ORR). ORR will be calculated as the number of participants with complete response (CR) or partial response (PR) by RECIST criteria, divided by the total number of participant in the dataset. The ORR will be estimated for every estimated and the associated exact 95% CI will be provided.

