## 8.6 Analysis Datasets

Analysis will be conducted on the modified intent-to-treat set (mITT), which includes all enrolled subjects treated with at least 1 dose (or partial dose) of the study medications. The mITT set will be used for all safety and preliminary efficacy analysis.

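### The population for the primary response rate is not settled: section 8.1 uses an undefined evaluable set, section 8.6 uses mITT, and following 8.1 could overstate ORR

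*Combined protocol and SAP*

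**What the plan says.** - **8.1 Introduction:** "The primary efficacy analysis will be conducted on the efficacy evaluable population and safety analysis will be performed on the safety evaluable population". Neither population is defined here or elsewhere.
- **8.6 Analysis Datasets:** defines one set, mITT, made up of enrolled subjects who received at least one full or partial dose. It then says: "The mITT set will be used for all safety and preliminary efficacy analysis".
- **8.5.1(b):** introduces the primary phase II endpoint with "To assess preliminary evidence of antitumor activity, in terms of Objective Response Rate (ORR" and computes it as CR plus PR "divided by the total number of participant in the dataset", with an exact 95% CI. The dataset is not named.
- **5.10 Subject Replacement Strategy:** of phase II patients who withdraw before response is assessed, it says "they will be replaced unless withdrawal is due to clinical disease progression". It does not say how a dosed, replaced patient is counted.
- **Sample size:** 8.4 says "27 patients are needed to detect an increase in RR" from 5% to 20%. Section 2.1 plans treatment "in up to 27 patients with metastatic MRP colon cancer" and 8.1 "in up to 27 patients with relapsed metastatic colon cancer". None says whether replaced patients count towards the 27.
- **Timing:** under section 6, footnote 10, the first on-study scan falls after cycle 3, about nine weeks in.

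**The concern.** The primary result is a single proportion from an open-label, single-arm trial, read against a 5% historical rate. No control arm would absorb a change of denominator.

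Two statisticians could each follow this plan and report different primary ORRs. One would take 8.1, supply a definition of evaluable (most naturally, at least one post-baseline response assessment) and exclude dosed patients who left before the first scan. The other would take 8.6 and keep them as non-responders. A patient with no post-baseline scan cannot be a responder, so the first choice shrinks the denominator and leaves the numerator alone. Because treatment is open-label, a definition written late could be written with responses already visible.

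Patients who could be excluded:

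- Those who withdraw or are lost before the first scan, whom 5.10 replaces.
- Clinical progressors who stop before a scan. Section 5.10 does not replace them, but that does not put them inside an undefined evaluable set.
- Possibly those who stop early for toxicity. Sections 5.9, 7.1.5 and 7.2.12 end disease follow-up when new anti-cancer therapy starts, whereas Appendix 11.4 continues imaging regardless of later therapy. Whether such patients would have a scan is therefore unclear.

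**Working it through.** **Inputs.** Null rate 5%, alternative 20%, 80% power, alpha 0.05, N = 27 (8.4); exact 95% CI (8.5.1(b)). The number k of dosed phase II patients without a post-baseline scan is not in the documents. I assume k = 1 to 6.

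**1. The plan's own figure.** With an exact binomial test at one-sided 0.05, the smallest N with 80% power is 27, with success at 4 or more responders: P(X≥4 | 27, 0.05) = 0.0437 and P(X≥4 | 27, 0.20) = 0.818. So 27 is reproduced. The plan itself states no test, cut-off or sidedness.

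**2. Following 8.1, with replacement up to 27 evaluable.** With x responders, ORR is x/27 if the k patients are dropped and x/(27+k) if they are kept. For x ≥ 1 the ratio is (27+k)/27.

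| k | factor | a true 20% reads as |
|---|---|---|
| 1 | 28/27 = 1.037 | 20.7% |
| 3 | 30/27 = 1.111 | 22.2% |
| 6 | 33/27 = 1.222 | 24.4% |

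For example, 4 responders with k = 3 gives 4/27 = 14.8% (95% CI 4.2 to 33.7) if dropped and 4/30 = 13.3% (3.8 to 30.7) if kept.

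**3. Following 8.1, with treated N staying at 27.** This applies if 27 is a cap on treated patients or the dropped patients are not replaced. The factor is 27/(27−k): 27/26 = 1.038 at k = 1 and 27/24 = 1.125 at k = 3.

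**4. Following 8.6.** All dosed patients stay in, so there is no inflation. If replacements are additional, treated N exceeds 27. A cut-off left at 4 would then have one-sided alpha 0.049 at N = 28, 0.055 at 29 and 0.061 at 30.

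**5. Type I error in case 2, illustrative only.** Suppose 5% is a rate per treated patient. The null rate among evaluable patients becomes 0.05 × (27+k)/27.

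| k | null rate | P(X≥4 of 27) | P(X≥5 of 27) |
|---|---|---|---|
| 0 | 0.0500 | 0.044 | 0.010 |
| 1 | 0.0519 | 0.049 | 0.012 |
| 2 | 0.0537 | 0.054 | 0.013 |
| 3 | 0.0556 | 0.060 | 0.015 |

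The 5-responder column corresponds to the planned exact 95% CI lying wholly above 5%: the lower limit is 4.2% for 4/27 and 6.3% for 5/27. If 5% is instead a rate per evaluable patient, type I error is not inflated. The documents do not say which it is. Section 4.2.1 reports one response among 97 treated patients but does not tie that to the 5%.

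**The case against.** The strongest reply is that the plan largely answers the question. Section 8.6 is the dedicated datasets section and defines the only set that can be implemented. Section 8.5.1(b) describes ORR as preliminary evidence of activity, which matches the wording 8.6 uses for mITT. Against this stands one sentence in an introduction. Replacement under 5.10 is an enrolment rule, and 8.6 makes no exception for replaced patients, so on its terms a dosed, replaced patient already stays in. All of this stands, and it makes mITT the better reading. It does not remove the conflict, because 8.1 speaks specifically of the primary efficacy analysis and nothing ranks the two sections.

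A reader might go further and infer that the replacement rule by itself inflates the primary ORR. The documents do not support that: under 8.6 there is no inflation. Nor must exclusion always raise ORR, since with no responders it is 0% either way. At a true 5%, 0.95^27 = 0.25, so that outcome is not remote.

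A reader might also infer that the trial's type I error exceeds 0.05. That needs 8.1 to prevail, evaluability to exclude these patients, 5% to be a per-treated rate, and a 4-of-27 rule that the plan never states. The plan is descriptive with an exact CI, and on a CI criterion error stays at 0.010 to 0.015 for k = 0 to 3.

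**Conclusion.** The conflict over the primary denominator is real and should be fixed. mITT is the better reading, and under it the estimate is not inflated. Under 8.1, with a definition that requires a response assessment, ORR is overstated by (27+k)/27 when 27 evaluable patients are reached and at least one responds. That is small for one or two patients and 11% relative for three. The size rests on k, which is assumed. The error rates illustrate a decision rule the plan does not contain, and should not be cited as properties of the trial. On either reading it remains open whether the limit of 27 counts replaced patients.

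**What to change.** - **8.1:** replace both evaluable-population terms with *the mITT set (section 8.6)*. Keep the existing tabulation by phase, so that phase I response is still reported.
- **8.5.1(b):** name the mITT set in place of the unnamed dataset, state that the primary phase II ORR uses the phase II mITT patients, and count a treated patient with no post-baseline scan as a non-responder.
- **5.10:** confirm that a dosed, replaced patient stays in the mITT denominator. State whether the limit of 27 includes replaced patients.
- **Sensitivity:** any evaluable-only ORR is reported as such, with its definition written down beforehand.
- **Cut-off, if one is used:** match it to the actual treated N. At one-sided 0.05 (sidedness is my assumption) this means at least 4 responders for N = 27 or 28, and at least 5 for N = 29 to 40.

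The cost is wording in three sections, with no new data or visits. ORR may be slightly lower, and some power may be lost if a matched cut-off is used. With 20% true among treated patients, power is 0.818 at 4 of 27, 0.716 at 5 of 29, 0.745 at 5 of 30 and 0.818 again at 5 of 33. If 20% holds only among evaluable patients and 10% leave unscanned (an assumption), the treated rate is 0.9 × 20% = 18%, and power is 0.742 at 4 of 27 or 0.649 at 5 of 30.
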